8.2 Endpoints Definitions

8.2.1 Safety Endpoints

- Primary Safety Endpoint

The primary safety endpoint will be time to first occurrence of confirmed major bleeding.

- Secondary Safety Endpoints

The secondary safety outcome for this trial is a composite of confirmed major bleeding and confirmed clinically significant non-major bleeding. Other safety outcome measures will also be assessed, and will include minor bleeds, fractures and other AEs as well as abnormal standard clinical laboratory test results. All major bleeding and clinically relevant non-major bleeding outcomes will be adjudicated by the CEC.

8.2.2 Efficacy Endpoints

- Primary Efficacy Endpoint

The primary efficacy endpoint will be the time to first occurrence of confirmed stroke (ischemic, hemorrhagic, or of type uncertain) or systemic embolism.

- Secondary Efficacy Endpoints

The secondary efficacy endpoints will be time to first occurrence of confirmed:

- ischemic stroke or stroke of unspecified type
- hemorrhagic stroke
- systemic embolism
- all cause death
- composite of stroke (ischemic, hemorrhagic, or of unspecified type), systemic embolism, major bleeding

[name]

25

- composite of stroke (ischemic, hemorrhagic, or of unspecified type), systemic embolism, all cause death
- composite of stroke (ischemic, hemorrhagic, or of unspecified type), systemic embolism, major bleeding, all cause death
- composite of stroke (ischemic, hemorrhagic, or of unspecified type), systemic embolism, myocardial infarction, all cause death
- composite of stroke (ischemic, hemorrhagic, or of unspecified type), systemic embolism and major bleeding in warfarin naïve subjects

All efficacy outcomes will be adjudicated by the CEC.

8.3 Analysis

8.3.1 Demographics and Baseline Characteristics

Frequency distribution and summary statistics for demographic and baseline variables will be presented by treatment group and for all subjects combined. Key demographic and baseline variables to be summarized include: geographic region, age, gender, race, height, weight, body mass index, vital signs (systolic blood pressure, diastolic blood pressure, and heart rate), prior warfarin / VKA status (experienced, naïve), risk factor type, number of risk factors, smoking history, baseline medications, atrial fibrillation type and onset.

8.3.2 Efficacy and Safety Analysis

To begin with, all subjects should be included in the groups to which they will be randomly assigned. This is an "intention to treat" analysis. If the result is statistically significant then will be applied per protocol analysis which should have the same results in intention to treat analysis.

Efficacy Analysis

Primary Censoring Scheme for Efficacy Endpoints

Subjects who do not experience an efficacy endpoint event will be censored at the earlier of their death date (when death is not part of the endpoint), last contact date (for subjects who withdraw consent to be followed up or are lost to follow-up) or the efficacy cut-off date. For endpoints other than all-cause death, the last contact date will be the last date on which the efficacy endpoint can be assessed. For instance, if a subject is only followed for survival status after date X, then date X will be the last contact date in the censoring scheme. For the all-cause death endpoint, the latest date on or prior to the efficacy cut-off date at which survival status can be determined will be used either as the date associated with the endpoint (if the subject died) or the censoring date (if the subject was determined to be alive).

- **Primary Efficacy Analysis**

The primary efficacy endpoint will be the time to first occurrence of confirmed stroke (ischemic, hemorrhagic, or of unspecified type), or systemic embolism during the study, regardless of whether the subject is receiving treatment at the time of the event. The primary objective is to determine if apixaban is non-inferior to warfarin for the primary efficacy endpoint. To conclude non-inferiority it will be necessary to demonstrate that the apixaban event rate for the primary endpoint is not materially higher than the warfarin event rate as measured by the relative risk of apixaban relative to warfarin.

The non-inferiority margin is 1.88 or 1.38 (ie, the margin is the midpoint between 1.0 and 1.88 on a log scale rather than linear scale because the primary parameter estimated is the logarithm of the relative risk)

Tests using each non-inferiority margin will be performed using a Cox proportional hazards model including treatment group as a covariate and stratified by prior warfarin / VKA status (experienced, naïve).

- **Key Secondary Analysis**

For the regulatory claims associated with the primary and the key secondary objectives listed, the following hierarchical testing procedure will be used:

[name]

26

Non-inferiority for the primary efficacy endpoint will be assessed first. If non-inferiority (using a non-inferiority margin of 1.38) is demonstrated then:

I. superiority for the primary efficacy endpoint will be tested

II. if superiority for the primary efficacy endpoint is

-not demonstrated, then stop

-demonstrated, then non-inferiority for major bleeding will be tested

III. if non-inferiority for major bleeding is

- not demonstrated, then stop

- demonstrated, then superiority for all cause death will be tested.

Safety Analysis

- **Primary Safety Analysis**

The primary safety endpoint will be time to first occurrence of major bleeding during the treatment period. A point estimate and two-sided 95% CI for relative risk and a p-value for the test of equality of rates ($RR = 1$) will be calculated. The test will be performed using a Cox proportional hazards model including treatment group as a covariate and stratified by prior warfarin status (experienced, naïve). Kaplan- Meier methodology will be used to estimate event rates over time. Subjects without events during the treatment period will be censored.

- **Secondary Safety Analysis**

The incidence of confirmed major bleeding events, confirmed clinically relevant non-major bleeding events, minor bleeding events and all bleeding AEs occurring through the end of the treatment period will be summarized by treatment group.

The incidence of AEs and of marked abnormalities in clinical laboratory tests will be summarized by treatment group. All AEs that are serious or that result in discontinuation of study drug will be described in depth

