3.2 Informed Consent

Investigators must ensure that subjects, or, in those situations where consent cannot be given by subjects, their legally acceptable representatives, are clearly and fully informed about the purpose, potential risks, and other critical issues regarding clinical studies in which they volunteer to participate. Freely given written informed consent must be obtained from every subject, or, in those situations where consent cannot be given by subjects, their legally acceptable representatives, prior to clinical trial study participation, including informed consent for any screening procedures conducted to establish subject eligibility for the study trial.

Subjects unable to give their written consent (e.g., stroke subjects, or subjects with severe dementia) may only be enrolled in the study with the consent of a legally acceptable representative. The subject must also be informed about the nature of the study to the extent compatible with the subject's understanding, and should they become capable, personally sign and date the consent form as soon as possible. The explicit wish of a subject unable to give his or her written consent, who is capable of forming an opinion and assessing this information to refuse participation in, or to be withdrawn from, the clinical study at any time should be considered by the Investigator.

[name]

11

For minors, according to local legislation, one or both parents or a legally acceptable representative must be informed of the study procedures and must sign the informed consent form approved for the study prior to clinical study participation. The explicit wish of a minor who is capable of forming an opinion and assessing this information to refuse participation in or to be withdrawn from, the clinical study at any time should be considered by the Investigator.

In order to successfully maintain the safety objectives of this endpoint driven trial, it is necessary that each subject's follow-up and vital status be maintained through to the end of the study. All reasonable efforts must be made to locate subjects to determine and report their current and ongoing status. The rights, safety, and well-being of the study subjects are the most important considerations and should prevail over interests of science and society.

UNIT 4 : Investigation Plan

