At the INR visits, only INR monitoring with POC device, assessment of outcomes, and assessment of study medication compliance will be performed. In addition, at the quarterly visits during the treatment period (Months 3, 6, 9, 15, 18, 21, 27, 30, 33, 39, 42, 45, 51, 54, 57) assessment of changes in concomitant medication, vital signs and laboratory assessments will be performed and at the yearly visits during the treatment period (Months 12, 24, 36, and 48) physical measurements and a 12 lead ECG will be obtained, and electrocardiograms will be performed. All subjects will be followed for the development of stroke (hemorrhagic, ischemic or unspecified), systemic embolism, myocardial infarction, death, bleeding, hospitalization or treatment discontinuation until the end of the study. Follow-up of subjects who discontinued study drug prior to the attainment of 433 primary events in the study should occur quarterly by a telephone call: the final follow-up visit should be in-person, if at all possible, and should be performed within approximately 30 days after the attainment of 433 primary efficacy events in the study.

SAEs (that occurred within 30 days after the last study dose of double-blind study drug) and study outcomes will be documented at all follow-up contacts.

There are three study periods expected to last up to of 60 months in duration:

(1) a screening period of up to 14 days, (2) a treatment period lasting until the earlier of a subject's treatment

[name]

12

discontinuation and the attainment of 433 primary efficacy events and (3) a follow-up period lasting until the latter of 30 days after treatment discontinuation or the attainment of 433 primary efficacy events.

Expected duration of the study, from first subject first visit through last subject, last visit is approximately 60 months.

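### Read literally, the censoring rule for the three secondary composites containing death counts deaths during survival-only follow-up but censors survivors in the same status when that follow-up begins

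*Protocol*

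**What the plan says.** Four statements in Protocol section 8.3.2 (Primary Censoring Scheme for Efficacy Endpoints) decide the matter.

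- Who is censored: "Subjects who do not experience an efficacy endpoint event will be censored at the earlier of their death date", the last contact date or the efficacy cut-off date. A subject who has an event gets no censoring date.
- When death censors: only "when death is not part of the endpoint". Where death is a component, it is an event.
- Last contact: "For endpoints other than all-cause death, the last contact date will be the last date on which the efficacy endpoint can be assessed". The example given is survival-only follow-up: "if a subject is only followed for survival status after date X, then date X will be the last contact date".
- All-cause death alone: "the latest date on or prior to the efficacy cut-off date at which survival status can be determined will be used", both as the event date for those who died and as the censoring date for those alive.

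Section 8.2.2 lists three composites that contain death: "composite of stroke (ischemic, hemorrhagic, or of unspecified type), systemic embolism, all cause death"; the same with major bleeding added; and stroke, systemic embolism, myocardial infarction and all-cause death. All three are endpoints other than all-cause death, so X is their last contact date.

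Deaths after X are likely to be known, because section 3.2 asks that each subject's follow-up and "vital status be maintained through to the end of the study".

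**The concern.** For the three composites, take two subjects who enter survival-only follow-up on the same day X. One dies a year later. Death is a component, so this subject has had an event, receives no censoring date and stays in the risk set until death. The other is alive at the cut-off, has had no event and is censored at X. After X, the only members of this group still at risk are those who will die.

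Cox regression and Kaplan-Meier estimation need censoring that does not depend on the future outcome, and this rule breaks that condition. It adds deaths without the matching survivor time, which raises the composite rate in each arm. If the arms differ in the share of subjects followed only for survival, the hazard ratio moves against the arm with the larger share.

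**Working it through.** **Applying the rule to each type of endpoint**

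| Endpoint | Dies after X | Alive after X | Same treatment? |
|---|---|---|---|
| Primary (stroke or systemic embolism) | censored at X, the earlier of X and death | censored at X | yes |
| All-cause death alone | event at death | censored at last date known alive | yes |
| Three composites with death, literal reading | event at death | censored at X | no |

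**Size.** The plan has no figure of its own on this point to reproduce. The target of 433 events belongs to the primary endpoint, which does not contain death, and is unaffected.

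Inputs from the Protocol (section 8.1): follow-up T = 2.3 years; non-fatal event rate λ = 1.2 per 100 patient-years; 7,843 subjects per arm.

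Assumptions, none of them in the Protocol: death rate μ of 2 to 5 per 100 patient-years; death rate after X equal to k times μ, with k from 1 to 3; a share s entering survival-only follow-up over 2.3 years if no event intervenes, at constant rate θ = -ln(1 - s)/T; constant hazards; true hazard ratio 1. The hazard ratio is taken as the ratio of the two arms' event rates.

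Per randomized subject, with h = λ + μ + θ:

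- Person-time up to X: PT = (1 - exp(-hT))/h
- Events up to X: E = (λ + μ) × PT
- Deaths after X: D = θ ∫₀ᵀ exp(-ht) [1 - exp(-kμ(T - t))] dt
- Time lived after X by those who die: P, by the same integration
- Rate if everyone stops at X: E/PT = λ + μ
- Rate under the literal rule: (E + D)/(PT + P)

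Worked case, μ = 3.5 per 100 patient-years and k = 1:

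- s = 5%: θ = 0.0223, h = 0.0693, PT = 2.126, E = 0.0999, D = 0.00191, P = 0.00146. Everyone stopped at X gives 4.70 per 100 patient-years. The literal rule gives (0.0999 + 0.00191)/(2.126 + 0.00146) = 4.79, an inflation of 1.8%. In one arm that is 7,843 × 0.00191 ≈ 15 extra deaths on top of 7,843 × 0.0999 ≈ 784 events.
- s = 3%: PT = 2.148, E = 0.1009, D = 0.00114, P = 0.00087. The literal rule gives 4.75, an inflation of 1.1%.
- 3% vs 5%: 4.751/4.786 = 0.993, where the truth is 1.

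Hazard ratio under the literal rule, with the smaller share in the numerator:

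| Shares | μ = 2, k = 1 | μ = 3.5, k = 1 | μ = 3.5, k = 2 | μ = 3.5, k = 3 | μ = 5, k = 3 |
|---|---|---|---|---|---|
| 3% vs 5% | 0.994 | 0.993 | 0.986 | 0.980 | 0.979 |
| 5% vs 8% | 0.990 | 0.989 | 0.979 | 0.970 | 0.968 |
| 4% vs 4% | 1.000 | 1.000 | 1.000 | 1.000 | 1.000 |

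Over the same range of μ and k, a 3% share inflates the rate by 0.9% to 3.2%, and a 5% share by 1.6% to 5.4%.

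For scale, the worked case has about 1,600 events in all (784 + 15 in one arm, 792 + 9 in the other), so the standard error of the log hazard ratio is about 2/√1600 = 0.05. The shift ln(0.993) = -0.007 is about 0.15 of that.

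**The alternatives.** Stopping everyone at X gives 1.000 throughout this model. Counting later deaths and also carrying survivors to the last date known alive gives 0.98 to 1.01 for the same two pairs of shares. It is not exactly 1, because non-fatal events after X go unseen and mortality after X may differ from mortality before it.

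**The case against.** The strongest reply is that section 8.3.2 never says a death after X counts in a composite. It defines last contact as the last date on which the endpoint can be assessed, and once only survival is followed the composite cannot be assessed in full. On that view X ends observation for everyone, and later survival information serves the all-cause-death endpoint alone, the only one for which it is mentioned. That reading has no such bias, and it stands as a possible reading. It is not stated, however. The sentence on who is censored points the other way, and nothing tells a programmer to discard a known death from an endpoint that contains death. Derivation details may be left to a SAP, but here the Protocol itself sets the rule, and as set it allows two event counts.

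Two further points stand. The trial is double-blind and double-dummy, and the Protocol gives no reason to expect unequal survival-only shares, so the differences used above are illustrations. The three composites also fall under the other secondary objectives in section 2.2 and outside the hierarchy in section 8.3.2.

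A reader might go further in three ways that the document does not support.

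- That everyone who withdraws from treatment is affected. Section 4.1 says "Follow-up of subjects who discontinued study drug prior to the attainment of 433 primary events in the study should occur quarterly by a telephone call", and outcomes are documented at all follow-up contacts. Only subjects followed solely for vital status matter.
- That the trial's type I error is inflated. These composites carry no confirmatory claim, so there is no controlled error rate to exceed.
- That the main result is at risk. The primary endpoint and all-cause death treat deaths and survivors alike.

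**Conclusion.** The concern holds as a defect in the literal wording for three secondary composites. Under that wording censoring depends on the outcome. The direction is certain; the size depends on survival-only shares and death rates that the Protocol does not give. Under the assumptions above, the composite rate rises by about 1-5% when 3-5% of subjects are in survival-only follow-up. A true hazard ratio of 1 moves to about 0.97-0.99 for shares of 3% vs 5% or 5% vs 8%, in favour of whichever arm has the smaller share. With equal shares and no true effect, only the rates are inflated. The effect is modest, but it comes from the rule itself and is easily removed before any data are seen.

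**What to change.** Add to section 8.3.2 that, for composites including all-cause death, observation ends at X for every subject: components dated on or before X count, death included, and everyone else who enters survival-only follow-up is censored at X.

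Add one sensitivity analysis that counts deaths after X and also keeps survivors at risk to the last date they are known to be alive. The two parts must go together, since counting the deaths without the survivor time recreates the problem.

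The cost is two sentences and one extra run. The downside is that a few deaths leave the main composite analyses, but they remain in the all-cause-death endpoint. Sample size, the primary analysis and the hierarchy do not change.

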1.1 Atrial fibrillation

Atrial fibrillation (AF) is the most common chronic arrhythmia globally. In the United States the prevalence of AF is 0.9%, or about 2.3 million persons, but this increases with advancing age, with over 10% percent of persons aged 80 or older affected. The prevalence of the disease is expected to double in the next 25 years as the population continues to age; the life time risk of developing AF is 1 in 4 for adults 40 years of age or older. Patients with AF suffer from a number of medical complications, but chief among these is stroke. AF leads to the formation of thrombus in the fibrillating left atrium, which can then embolize into the systemic circulation resulting in stroke or systemic embolization. AF is a major cause of stroke and is responsible for 15 - 20% of all strokes. In persons over the age of 80, AF is the leading cause of stroke, and such strokes are particularly devastating in the elderly, where they are a major cause of both morbidity and mortality.

In the past 20 years, there have been significant advances in our understanding of AF, its causes, treatment and complications. Although new antiarrhythmic drugs and ablation techniques have been introduced, a mainstay of therapy for AF at present is anticoagulation with warfarin or other vitamin K antagonists (VKAs) to prevent stroke and systemic embolism. The VKAs, of which warfarin is the most common example, have been in use for over 50 years. All of these compounds exert their anticoagulant effect by antagonizing the vitamin K dependent epoxidation cycle; all are monitored by means of the international normalized ratio (INR).

Warfarin has been demonstrated to be effective in reducing the risk of stroke in subjects with AF, with an impressive relative risk reduction (RRR) of 62% (95% CI, 48% to 72%) when compared to placebo.

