8.1 Sample Size Estimation

The primary efficacy endpoint will be the time to first occurrence of confirmed ischemic stroke, hemorrhagic stroke, stroke of unspecified type or systemic embolism, regardless of whether the subject is receiving treatment at the time of the event. The primary objective is to determine if apixaban is non-inferior to warfarin for the primary efficacy endpoint.

A key aspect of developing the adequate sample size for this trial is arriving at the appropriate non-inferiority margin. Warfarin has been studied in 6 different placebo controlled randomized trials in subjects with AF. There is a meta-analysis for these studies.

The relative risk reduction of warfarin compared with placebo in these trials using a random effects model was 0.36 (95% CI 0.24-0.53), such that the inverse of the upper boundary (ie, control compared with warfarin) is 1.88 (1/0.53). To establish that at least half of the warfarin effect is preserved, the noninferiority margin is 1.88 or 1.38 (ie, the margin is the midpoint between 1.0 and 1.88 on a log scale rather than linear scale because the primary parameter estimated is the logarithm of the relative risk)

Defining a treatment effect on the log scale seems arguably more sensible statistically and mathematically for one basic reason. Suppose that the risk ratio C/P is 0.53, which amounts to a $1-0.53=0.47 = 47\%$ reduction of risk by the control relative to the placebo. But, by inversion, $P/C = 1/0.53 = 1.88$ which amounts to a 88% increase by the placebo relative to the control. The 47% decrease is not equal to the opposite of the 88% increase. This awkward difference may cause difficulty in interpretation of a treatment effect. Defining a treatment effect on the log risk ratio scale will avoid the difficulty because $\log C/P = -\log P/C$ and thus the effect of C vs. P differs from the effect of P vs. C only by sign.

Using the meta-analysis for these 6 studies is showed that the events/patient-year for warfarin is 2.38 %. So, the events/patient-year for apixaban is $1.38 * 2.38 = 3.28\%$.

It is set that the duration of the study is 2.3 years. From the literature it is known that the number of the strokes is 1.2 / 100 patient-years.

As a result the sample size for power 90% , p-value 5% and $\Delta = 3.28-2.38=0.9\%$ is

$$n \geq \left(\frac{p_1^{*(1-p_1)} + p_2^{*(1-p_2)}}{D^2} \right) * (1.96 + 1.28)^2$$

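### The non-inferiority margin of 1.38 is not the log-scale midpoint from which the protocol derives it (1.371), and it falls just short of the stated half-preservation of warfarin's effect

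*Protocol*

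**What the plan says.** Section 8.1 takes the warfarin effect from a meta-analysis of six placebo-controlled trials: "The relative risk reduction of warfarin compared with placebo in these trials using a random effects model was 0.36 (95% CI 0.24-0.53"). It inverts the upper limit: "the inverse of the upper boundary (ie, control compared with warfarin) is 1.88 (1/0.53"). It then sets the margin: "To establish that at least half of the warfarin effect is preserved, the noninferiority margin is 1.88 or 1.38", explained as the log-scale midpoint of 1.0 and 1.88. Section 8.3.2 repeats this: "The non-inferiority margin is 1.88 or 1.38 (ie, the margin is the midpoint between 1.0 and 1.88 on a log scale".

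The same section goes on: "Tests using each non-inferiority margin will be performed using a Cox proportional hazards model". The hierarchical procedure opens on a single value: "If non-inferiority (using a non-inferiority margin of 1.38) is demonstrated then". The synopsis makes the same statements under its sample-size and efficacy-analysis paragraphs.

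The 1.38 is also an input to the sample size in Section 8.1. Multiplied by the warfarin rate of 2.38% per patient-year it gives 3.28%, hence a difference of 0.9 percentage points, 7,130 per arm, and 7,843 after 10% is added.

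**The concern.** The margin is the pass/fail threshold of the primary test and the gate to every later claim, so it should be reproducible from the derivation printed beside it. It is not, and the discrepancy is in the permissive direction. An upper confidence limit between 1.374 and 1.38 would be reported as showing that half or more of warfarin's effect is kept, when the protocol's own figures say slightly less than half.

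Two wording faults make the rule harder to read. Tests for each margin imply more than one, while the hierarchy uses one. And 0.36 (0.24 to 0.53) is called a relative risk reduction, although Section 8.1 itself treats 0.53 as a risk ratio, equivalent to a 47% reduction. Taken at its label, the figure would mean a 36% reduction.

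**Working it through.** **Inputs.** Relative risk 0.36 with upper limit 0.53, its inverse 1.88, the log-midpoint rule, the preservation criterion, margin 1.38, warfarin rate 2.38%, and z-values 1.96 and 1.28 (Section 8.1); 1:1 allocation (Section 5.3); 433 events (Section 4.1).

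**1. The margin.** Log midpoint of 1 and U = exp((ln 1 + ln U)/2) = √U.

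- U = 1.88 (as printed): √1.88 = 1.371
- U = 1/0.53 = 1.8868: 1.374
- U = 1.89 (1/0.53 to two decimals): 1.375, unrounded 1.3748
- Linear midpoint, (1 + 1.88)/2: 1.44

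None gives 1.38. To obtain exactly 1.38, U must be 1.38² = 1.904, an upper limit of about 0.525.

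**2. Share of effect preserved** = 1 − ln(margin)/ln(U).

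| Reference effect | Margin 1.38 | Margin 1.37 |
|---|---|---|
| U = 1.88 (ln = 0.6313) | 1 − 0.3221/0.6313 = 49.0% | 1 − 0.3148/0.6313 = 50.1% |
| U = 1/0.53 (ln = 0.6349) | 49.3% | 50.4% |
| Point estimate, 1/0.36 (ln = 1.0217) | 68.5% | 69.2% |

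**3. Effect on the primary test.** With 433 events and 1:1 allocation, the standard error of the log hazard ratio is about 2/√433 = 0.0961.

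- False passes at 1.38 if the true hazard ratio is 1.371: Φ((ln 1.38 − ln 1.371)/0.0961 − 1.96) = Φ(−1.89) = 2.9%. At 1.374 it is 2.8%. The nominal value is 2.5%.
- Power if the true hazard ratio is 1, margin 1.38: Φ(0.3221/0.0961 − 1.96) = Φ(1.391) = 91.8%.
- The same at margin 1.37: Φ(0.3148/0.0961 − 1.96) = Φ(1.315) = 90.6%.

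**4. Effect on the stated sample size.** The protocol's formula is n = [p₁(1−p₁) + p₂(1−p₂)]/D² × (1.96 + 1.28)².

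- Its own figure first: with its rounding, 0.055/0.000081 × 10.5 = 7,129.6, which reproduces 7,130; without intermediate rounding, 7,122.5.
- With 1.37: p₂ = 1.37 × 0.0238 = 0.032606, D = 0.008806, and n = 0.054776/0.008806² × 10.4976 = 7,415 per arm. Adding 10% gives 8,157, against 7,843.
- Power of the planned numbers under the same formula at 1.37, Φ(√(nD²/0.054776) − 1.96): 91.5% if all 7,843 per arm count and 88.8% if only 7,130 do.

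**The case against.** The strongest defence is rounding. The 0.53 is a two-decimal figure, and an underlying limit between 0.525 and 0.5289 would print as 0.53 and give a midpoint that rounds to 1.38. The source is not at hand, so 1.38 may have been carried from unrounded inputs. This could explain the number, but it does not rescue the derivation, which works from 1.88 and 1/0.53. Moreover, 1.38 itself preserves a full half only if the limit is at or below 1/1.38² = 0.5251.

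It is also fair to say that the shortfall exists only against the conservative confidence bound. That bound is the protocol's own choice, so the criterion is missed on its own terms, but the size must be stated with that qualifier.

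A reader might infer from "To establish that at least half of the warfarin effect is preserved, the noninferiority margin is 1.88 or 1.38" that 1.88 is a second margin, so that a drug no better than placebo could be called non-inferior. The documents do not support this. The parenthesis describes a single midpoint, and the phrase makes sense as the root of 1.88, or 1.38, with the root sign probably lost when the PDF was read. The hierarchy and the sample size use 1.38 alone, so passing at 1.88 would unlock nothing. What stands is the stray reference to each margin.

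A reader might also see a contradiction with Section 1.1, which cites a "relative risk reduction (RRR) of 62% (95% CI, 48% to 72%) when compared to placebo". That is background, with no trials or model named, while Section 8.1 says which estimate the margin rests on. The two may differ without error.

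**Conclusion.** The printed margin does not follow from the printed rule: 1.371 (or 1.374) against 1.38. Measured as the protocol measures it, 1.38 preserves 49.0% to 49.3% of warfarin's effect and so just misses the stated criterion. The reference to each margin and the mislabelled relative risk are real but minor wording faults.

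The consequence is small. The false-pass rate at the half-preservation boundary is 2.8% to 2.9% rather than 2.5%, and if the true hazard ratio is 1 the choice between 1.38 and 1.37 moves power by about one percentage point. These figures assume 433 events, equal allocation and the usual large-sample variance of the log hazard ratio.

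One should not conclude that 1.38 gives away most of warfarin's benefit, or that correcting it leaves the trial underpowered; neither follows. Severity is moderate: the threshold of the primary test should match its justification before data are seen, but the design does not depend on it.

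**What to change.** State one margin, 1.37, in Sections 8.1 and 8.3.2 (primary analysis and hierarchical procedure) and in the matching synopsis paragraphs. Refer to the test at that margin rather than at each margin. Label 0.36 (0.24 to 0.53) a relative risk.

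Carry 1.37 through the calculation in Section 8.1 and the synopsis; otherwise margin and sample size will disagree. The protocol's formula then asks for about 7,415 per arm (8,157 with 10%). No extra enrolment is needed if the protocol does one of two things:

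- restates the power that the planned numbers give under that formula (91.5% with all 7,843 per arm, 88.8% with 7,130); or
- justifies power by the 433 events that end the trial, which give 90.6% at 1.37.

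Alternatively, keep 1.38 and replace the claim of half or more with a statement that about 49% of the lower-bound effect is preserved. That leaves the sample size untouched but concedes the criterion.

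The cost is a few consistent edits and, with 1.37, a fall in event-based power from 91.8% to 90.6%.
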